9.3 VARIABLES

9.3.1 Primary outcome

The primary outcome is the proportion of patients attaining blood glucose control target defined as HbA_{1c}<7%, according to 2015 American Diabetes Association (ADA) [\[R16-1532\]](#) and 2013 Chinese Diabetes Society (CDS) guidelines.

9.3.2 Secondary outcomes

Secondary outcomes are:

- Renal function of patients

- Estimated glomerular filtration rate (eGFR) evaluated by CKD Epidemiology Collaboration (CKD-EPI) equation expressed as:
$$GFR = 141 \times \min(Scr/\kappa, 1)^\alpha \times \max(Scr/\kappa, 1)^{-1.209} \times 0.993^{Age} \times 1.018 \text{ [if female]} \times 1.159 \text{ [if black]}$$

If SCr is in mg/dL, $\kappa = 0.7$ if female, $\kappa = 0.9$ if male
If SCr is in $\mu\text{mol/L}$, $\kappa = 61.9$ if female, $\kappa = 79.6$ if male
 $\alpha = -0.329$ if female
 $\alpha = -0.411$ if male
min = the minimum of Scr/ κ or 1
max = the maximum of Scr/ κ or 1
- Albuminuria categorized as micro-albuminuria and macro-albuminuria according to the definition in [Table 1](#).
- Treatment regimens for T2DM that the patients are currently taking, categorized as follow: (GLP-1 has been regard as OAD even though it's an injection treatment)
 - No treatment
 - Only diet control and exercise
 - Oral antidiabetic drug (OAD)-Mono therapy
 - Biguanide
 - α -glucosidase inhibitor
 - Sulfonylureas
 - Thiazolidinediones
 - Meglitindes
 - Dipeptidyl peptidase-4 (DPP-4) inhibitors
 - Sodium-glucose co-transporter (SGLT-2) inhibitors
 - Glucagon like peptide-1 (GLP-1) analogue
 - OAD-Combined therapy
 - Dual
 - Triple
 - Insulin only
 - OAD + Insulin
- Proportion of macro-vascular and micro-vascular diabetic complications:
 - Cardiovascular disease (i.e., coronary artery disease)
 - Cerebrovascular disease (i.e., ischemic stroke)
 - Peripheral vascular disease (i.e., diabetic foot)
 - Kidney disease (i.e., diabetes nephropathy)
 - Retinopathy
 - Neuropathy
- Proportion of Hypoglycaemic occurrence
- Proportion of Hypoglycaemia leading to therapy change
- Proportion of Anti-hypertension therapy usage
- Proportion of Lipid Lowering therapy usage
- Proportion of Anti-Platelet therapy usage
- Treatment adherence to Chinese T2DM guideline 2013
 - 0-3 month
 - 3-6 month
 - 6-12 month
 - >12 month

9.3.4 Safety events

All adverse drug reactions (ADRs) (serious and non-serious) and all AEs with fatal outcome (death) must be collected by the investigator from signing the informed consent onwards until the end of the study.

9.4 DATA SOURCES

Data will be newly collected from the patient by the investigator and recorded as source data at the site, i.e. the physician's records, and entered in the eCRF by the investigator or site staff.

9.5 STUDY SIZE

According to a recent study, the proportion of patients with diabetes in China who achieved a target blood glucose level of HbA_{1c} <7% was 39.8% in patients aged 60-69 years old and 38.9% in patients aged 70 years old or above ^[1]. It is assumed that the proportion of patients

attaining the target blood glucose level in the present study will be 39%. To ensure the accuracy of the estimate for proportion of patients with $HbA_{1c} < 7\%$, the length of a two-sided 95% confidence interval (CI) should not extend beyond 5%. A sample size of 1463 patients is required to achieve the expected accuracy. Assuming HbA_{1c} measurements are available for 97.5% of the enrolled patients, a total of 1500 patients will be recruited.

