4. ABSTRACT

Name of company: Boehringer Ingelheim			
Name of finished medicinal product: Not applicable			
Name of active ingredient: Not applicable			
Protocol date: 29 Sep 2016	Study number: 1218.174	Version/Revision: 2.0	Version/Revision date: 20 Dec 2016
Title of study:	Clinical characteristics, anti-hyperglycaemic treatment pattern and target attainment of type 2 diabetes mellitus patients in older population with or without albuminuria in China: A nationwide cross-sectional study		
Rationale and background:	China has the largest number of people with diabetes in the world, with the majority of the patient population over 60 years old and living in urban areas. However no data are available specifically on the clinical characteristics of the older population with type 2 diabetes mellitus (T2DM) in China		
Research question and objectives:	To investigate the level of glucose control, current anti-hyperglycaemic and the anti-hypertension/Lipid Lowering/anti-platelet treatment patterns, occurrence of the hypoglycaemia, and other potential factors associated with the level of glucose control in older population of T2DM in China		
Study design:	This is a multi-centre, cross-sectional, non-interventional study		
Population:	Outpatients with T2DM aged 60 years or older in China		
Variables:	
Primary outcome
 
 Proportion of patients attaining blood glucose control target defined as $HbA_{1c} < 7\%$ 
Secondary outcomes
 
 Renal function level of patients Treatment regimens for T2DM that patient are currently taking Proportion of macro-vascular and micro-vascular diabetic complications Proportion of Hypoglycaemic occurrence Proportion of Hypoglycaemia leading to therapy change Proportion of Anti-hypertension therapy usage Proportion of Lipid Lowering therapy usage Proportion of Anti-Platelet therapy usage Treatment adherence to Chinese T2DM guideline 2013 		
Data sources:	Examination report, outpatient medical Chart or other original medical record		
Study size:	1500 patients		

Proprietary confidential information © 2016 Boehringer Ingelheim International GmbH or one or more of its affiliated companies

Name of company: Boehringer Ingelheim			
Name of finished medicinal product: Not applicable			
Name of active ingredient: Not applicable			
Protocol date: 29 Sep 2016	Study number: 1218.174	Version/Revision: 2.0	Version/Revision date: 20 Dec 2016

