9.2 SETTING

9.2.1 Study population

In this cross-sectional study, approximately 1500 patients will be recruited. Older outpatients with T2DM will be selected consecutively from departments of endocrinology in at least 30 hospitals of China.

Figure 1 – Study Flow of the cross-sectional study

Inclusion criteria

- Patient should fully know and understand the content of consent form, and the patient is willing and able to sign an informed consent form
- Outpatient with confirmed T2DM (According to Definition and Diagnosis Diabetes Mellitus :World Health Organization 1999[R04-1142])
- Age ≥ 60 years

Exclusion criteria

- Patients with type 1 diabetes mellitus or secondary DM
- Patients who are participating in any other clinical study, including any questionnaire-based study, any interventional study (including diet/counselling

based intervention), or any clinical study in which any medications (including Chinese herbal medications) are administered

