9.2.2 Visit schedule

Patients will be recruited into the study in the order of their clinical visits scheduled. First 7 consented and suitable patients will be recruited for each site on each day, or fewer if without enough patients. One study visit is planned for each patient. Clinical assessments will be performed as part of routine clinical practice. Some laboratory tests results prior to the study can be used as source data as specified below. All data required should be entered into the Electronic Data Capture (EDC) System only after each patient has consented to participation.

During the study visit, the following procedures will be performed:

- Signature of informed consent and recording of the date informed consent was given
- Determination of eligibility by checking the inclusion/exclusion criteria
- Collect the following information
 - Demographic information
 - Personal health history
 - Diabetes Mellitus history
 - Chronic Kidney Disease history
 - Anti-Hypertension therapy history
 - Lipid Lowering therapy history
 - Anti-Platelet therapy history
 - hypoglycaemic history
 - Family health history (e.g., diabetes, hypertension, and Chronic kidney diseases)
 - Lifestyle
 - Physical examination
 - body weight
 - height
 - waist circumference
 - Vital sign
 - blood pressure
 - heart rate
 - Laboratory tests
 - HbA_{1c}
 - Albuminuria
 - Urine WBC
 - Fasting plasma glucose (FPG), (examined within one month prior to the visit)
 - Serum creatinine (SCr), uric acid (UA), high density lipoprotein cholesterol (HDL-C), low density lipoprotein cholesterol (LDL-C), triglyceride (TG), total cholesterol (TC) (If examined within three months prior to the visit, record the result; if examined without three

months prior to visit, record the date of last examination and re-examine by investigator's judgment.)

All of the laboratory tests will be performed by local laboratory and will be required on the same day of visit. The laboratory tests performed prior to the visit which can be used as source data are specified above.

Albuminuria can be measured in a random spot urine sample, a 24-h urine sample, or a timed urine sample. The results of albuminuria measurement will be categorized as normal, micro- and macro-albuminuria based on the definition in [Table 1](#).

Table 1 Definition of Albuminuria

Urinary albumin excretion	Random spot urine	24-h urine	timed urine
	ACR (mg/g)	24h UAE (mg/24h)	UAE (µg/min)
Normal	<30	<30	<20

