9.7.2 Primary analyses

The proportion of patients attaining blood glucose control target of $HbA_{1c} < 7\%$ will be summarized descriptively on FAS.

Detailed information about variable categorization will be specified in SEAP.

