7. PLANNED ANALYSIS

The following standard descriptive statistical parameters will be displayed in summary tables of all continuous variables:

N	number of non-missing observations
Mean	arithmetic mean
SD	standard deviation
Min	minimum
Median	median
Max	maximum

Tabulations of frequencies for categorical data will include all possible categories and will display the number of observations in a category as well as the percentage (%) relative to the respective treatment group (unless otherwise specified, all subjects in the respective subject set whether they have non-missing values or not). Percentages will be rounded to one decimal place. The category missing will be displayed only if there are actually missing values.

For logistic regression model, adjusted odds ratio with 95% confidence interval, and p-value will be provided for the factors involved.

All data processing, summarization and analyses will be performed using Version 9.2 (or later) of the SAS statistical software package (Windows OS).

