7.6 MAIN ANALYSES

The blood glucose control proportion (HbA1c<7%) will be tabulated on FAS – E.

The analyses for parameters below will be performed on both FAS – E and FAS – Albuminuria:

- Renal function variables (eGFR, albuminuria, and CKD staging) will be summarized
- The proportion of the occurrence of hypoglycaemia and the proportion of hypoglycaemia leading to therapy change will be summarized descriptively.

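### The 5-point confidence interval length that sets the sample size assumes independent patients, but patients are clustered in hospitals, and the visible primary analysis names no interval for the proportion

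*Protocol*

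**What the plan says.** Protocol 9.5 assumes that 39% of patients will have HbA1c below 7% and sets the precision target: "the length of a two-sided 95% confidence interval (CI) should not extend beyond 5" percent. It concludes: "A sample size of 1463 patients is required to achieve the expected accuracy". It then assumes HbA1c will be available for 97.5% of those enrolled and arrives at 1500. That is the only allowance in the calculation.

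On sampling, protocol 9.2.1 states: "Older outpatients with T2DM will be selected consecutively from departments of endocrinology in at least 30 hospitals of China". Section 9.2.2 caps recruitment at seven patients per site per day and adds: "All of the laboratory tests will be performed by local laboratory and will be required on the same day of visit". The title describes "type 2 diabetes mellitus patients in older population with or without albuminuria in China: A nationwide cross-sectional study".

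On the analysis, protocol 9.7.2 says the primary proportion "will be summarized descriptively on FAS", and SAP 7.6 says: "The blood glucose control proportion (HbA1c<7%) will be tabulated on FAS – E". The only interval named in the visible SAP is in the introduction to section 7: "For logistic regression model, adjusted odds ratio with 95% confidence interval, and p-value will be provided for the factors involved".

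**The concern.** Patients at one hospital share physicians, prescribing habits, a catchment population and a laboratory, so their HbA1c results may be correlated. Protocol 9.9 itself urges caution with HbA1c because it is not measured centrally. If the result is to speak for a nationwide population, the hospitals act as a sample of clusters, and differences between them add variance that the section 9.5 formula omits. The 5% length would then not be reached with 1500 patients.

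The second gap needs no assumption about correlation. Interval length is the only stated basis for the sample size, yet the sections that carry the primary analysis do not commit to reporting an interval. If a default binomial interval were added at reporting, it would be too narrow to the extent that hospitals differ.

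**Working it through.** **Inputs from the documents:** p = 0.39, full length L = 0.05, two-sided 95%, 1463 analysable, 1500 enrolled, 97.5% with HbA1c (all protocol 9.5); at least 30 hospitals (protocol 9.2.1).

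**Assumed, because the documents give no value:** ICC of 0.005, 0.01, 0.02 or 0.05; equal hospital sizes; 60 hospitals as an alternative to the minimum of 30.

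**1. The plan's own figure.** With z = 1.95996, n = z² × p(1−p) / (L/2)² = 3.8415 × 0.2379 / 0.000625 = 1462.2, rounded up to 1463. The length at 1463 is 4.999 points. The plan's number is therefore reproduced exactly, with a design effect of 1.

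**2. Slack.** 1500 × 0.975 = 1462.5, so the enrolment target only just delivers the required number. The 2.5% covers missing HbA1c only, whereas the FAS – E in SAP 6.3 also drops ineligible patients.

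**3. Break-even ICC.** Suppose all 1500 have HbA1c. The length under independence is 2 × 1.96 × √(0.2379/1500) = 4.937 points. The largest design effect compatible with 5 points is (5/4.937)² = 1.0258. Since DEFF = 1 + (m − 1) × ICC:
- 30 hospitals, m = 50: ICC = 0.0258/49 = 0.0005
- 60 hospitals, m = 25: ICC = 0.0258/24 = 0.0011

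**4. Length over the assumed range.** With 1463 analysable patients, m = 1463/30 = 48.8 or 1463/60 = 24.4. Length = 2 × c × √(0.2379 × DEFF/1463), where c is 1.96 (normal), or 2.045 (t, 29 df) and 2.001 (t, 59 df). Coverage of an unadjusted 95% interval is approximately 2Φ(1.96/√DEFF) − 1.

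| Hospitals | ICC | DEFF | Length, normal (points) | Length, t (points) | Coverage if unadjusted |
|---|---|---|---|---|---|
| 30 | 0 | 1.00 | 5.0 | 5.2 | 95% |
| 30 | 0.005 | 1.24 | 5.6 | 5.8 | 92% |
| 30 | 0.01 | 1.48 | 6.1 | 6.3 | 89% |
| 30 | 0.02 | 1.96 | 7.0 | 7.3 | 84% |
| 30 | 0.05 | 3.39 | 9.2 | 9.6 | 71% |
| 60 | 0 | 1.00 | 5.0 | 5.1 | 95% |
| 60 | 0.005 | 1.12 | 5.3 | 5.4 | 94% |
| 60 | 0.01 | 1.23 | 5.6 | 5.7 | 92% |
| 60 | 0.02 | 1.47 | 6.1 | 6.2 | 89% |
| 60 | 0.05 | 2.17 | 7.4 | 7.5 | 82% |

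The ICC 0 rows show what the t quantile alone adds: 0.2 point with 30 hospitals and 0.1 with 60. The rest is clustering. Unequal hospital sizes would lengthen the interval further.

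**5. Is an interval planned?** The SAP section 7 introduction lists N, mean, SD, minimum, median and maximum for continuous variables, and counts and percentages for categorical ones. It names an interval only for odds ratios. SAP 7.3 on bias is marked not applicable, and 7.4 deals only with confounders in the logistic model. Protocol 9.7.2 and SAP 7.6 name neither an interval for the proportion nor a method that uses hospital.

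**The case against.** The strongest reply is that this is a descriptive study. Protocol 9.7 calls all analyses exploratory, no hypothesis is tested, and nothing is decided on whether the interval is 5 or 7 points long. That stands, and it limits the severity. It does not remove the point, because in a descriptive study the estimate and its precision are the result, and precision is the only justification given for the sample size.

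Second, the size of the effect is assumed. Neither the ICC range nor the 60-hospital case comes from the documents, and 30 is a floor, so the 30-hospital rows are the least favourable. This also stands: the lengths are illustrative. The direction does not depend on them, because the break-even values are close to zero.

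Third, several SAP sections (4, 5.2, 6.4, 7.5, 7.7 and 9) and protocol 9.3.3 are not in the public text, and an interval or site-level method could be specified there. That cannot be excluded. But the sections that define the primary analysis, and the general conventions in SAP 7, are visible and are where such an interval belongs.

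Fourth, the coverage figures describe an unadjusted interval that the plan does not specify. That is correct; they show only what a default choice at reporting would do.

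Finally, the protocol does not say how hospitals are chosen. If they are not a random sample, a clustered interval does not by itself justify a nationwide claim. That is true, but treating the hospitals as fixed would confine the result to those hospitals, which is further from the title's claim.

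The possible loss of ineligible patients from the FAS – E is a minor matter. Eligibility is checked at the visit, and no ineligibility rate is given.

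**Conclusion.** The concern holds. The arithmetic in 9.5 is right under independence within hospital, but that condition is unstated and the design gives no reason to expect it. With 1500 patients, a normal-based interval exceeds 5 points at any ICC above about 0.0005 (30 hospitals) or 0.0011 (60). For assumed ICCs of 0.005 to 0.05, equal hospital sizes and 1463 analysable patients, the t-based length is 5.8 to 9.6 points with 30 hospitals and 5.4 to 7.5 with 60. In addition, the visible plan does not commit to any interval for the proportion on which the study was sized. This should be fixed. It affects how precisely readers believe the primary figure is known, not any decision rule.

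**What to change.** **Protocol 9.5:** keep 1500 patients. State that the 5% length assumes independent observations, and give the expected length of a hospital-clustered t-based interval over stated ICCs and numbers of hospitals: for ICC 0.005 to 0.05, about 5.8 to 9.6 points with 30 hospitals and 5.4 to 7.5 with 60. Note that the t quantile accounts for 0.2 and 0.1 point respectively, so that the comparison with 5% is fair.

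**SAP 7.6:** report the FAS – E proportion with a two-sided 95% confidence interval that treats hospital as the cluster (Taylor-linearised survey variance, t with number of hospitals minus 1 degrees of freedom), and report the estimated ICC.

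**Cost:** one sentence in each document and a survey procedure in SAS, which is already the planned software. No further patients or data are needed. The only drawback is that the stated precision becomes less favourable.

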9.6 DATA MANAGEMENT

All data generated by the site personnel will be captured electronically at each study centre using eCRFs. Data from external sources (such as laboratory data) will be imported into the database.

In order to maintain source documentation of the outpatient record, Investigators will have complete access to the data for their patients, thus facilitating quality improvement initiatives and single-centre research. Each investigator will be required to first report all patient data on the outpatient medical chart or other acceptable original medical record.

Local Clinical Research Associate (CRA) will conduct routine on-site monitoring of the original data quality and review the study material and data.

Data queries generated from the database will be created on an ongoing basis; queries will be based on the data management system logic deck and database validation for adequacy and consistency.

9.7 DATA ANALYSIS

All the following analyses are exploratory in nature and the p-values provided by these analyses will only be nominal. Missing data will not be imputed. Details of all analyses will be provided in the statistical and epidemiological analysis plan (SEAP).

9.7.1 Analysis population

The statistical analysis will be based on the following populations.

Full Analysis Set (FAS)

The FAS includes all patients with an HbA_{1c} measurement.

FAS – Albuminuria

The FAS – Albuminuria dataset is a subset of patients of FAS, which includes T2DM patients with albuminuria (micro-albuminuria without urinary tract infection based on urine WBC result and macro- albuminuria).

9.7.2 Primary analyses

The proportion of patients attaining blood glucose control target of $HbA_{1c} < 7\%$ will be summarized descriptively on FAS.

Detailed information about variable categorization will be specified in SEAP.

9.7.3 Secondary analyses

The analyses for following secondary outcomes will be performed on both FAS and FAS - Albuminuria as below:

- For renal function variables, eGFR and albuminuria, descriptive statistics will be calculated
- The treatment pattern for T2DM will be summarized descriptively with frequency and proportion,
- The proportion of the occurrence of hypoglycaemia and the proportion of hypoglycaemia leading to therapy change will be summarized descriptively.

Then for the other secondary outcomes, the analyses will only be performed on FAS:

- The proportion of each macro vascular and micro-vascular diabetic complications will be calculated.
- The proportion of using anti-hypertension therapy, lipid –lowering therapy, and anti-platelet therapy will be calculated respectively.
- The treatment adherence will be summarized using the proportion of each follow-up duration category.

9.8 QUALITY CONTROL

Once the eCRF clinical data have been submitted to the central server at the independent data centre, corrections to the data fields will be captured in an audit trail. The reason for change, the name of the person who performed the change, together with the time and date will be logged to provide an audit trail.

If additional corrections are needed, the responsible monitor or data manager will raise a query in the EDC application. The appropriate staff at the study site will answer queries sent to the investigator. The name of the staff member responding to the query, and time and date stamp will be captured to provide an audit trail. Once all source data verification is complete and all queries are closed, the monitor will freeze the eCRF page.

The specific procedures to be used for data entry and query resolution using the EDC system/eCRF will be provided to study sites in a training manual. In addition, site personnel will receive training on the EDC system/eCRF.

All the laboratory tests will be conducted in the qualified local clinical laboratory.

9.9 LIMITATIONS OF THE RESEARCH METHODS

Some limitations are unavoidable given the design of this cross-sectional study; however, this study will generate substantial new knowledge that applies to the real-world clinical setting.

Secondly, due to cross-sectional nature of our study, there may be potential reverse causation bias. Therefore the data need to be interpreted with cautions.

A further limitation of the study is that albuminuria is estimated based on a single measurement. Hence, no data on the reproducibility of the urinary albumin excretion measurements will be available. Moreover, the data regarding HbA_{1c} will have to be interpreted with caution as blood measurement are not performed at central laboratory.

